**a) Oral PrEP**

- Discontinuation: any discontinuation, resumption of oral PrEP after discontinuation  
Two durations will be used to identify discontinuation of oral PrEP:
  - o Oral PrEP prescription not refilled within 30 days of the previous dispensing
  - o Oral PrEP prescription not refilled within 90 days of the previous dispensing
- Duration of oral PrEP use for the first period of use

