    - Incidence proportion and incidence rate of HIV testing between the start of PrEP and the first discontinuation
    - Timing of HIV tests:
      - Oral PrEP: on-schedule testing defined as receiving an HIV test  $\leq 7$  days before/at start, and 3 months (76-104 days) after each test
      - CAB LA PrEP: on-schedule testing defined as receiving an HIV test

≤7 days before/at first injection, and 14 days prior each subsequent injection

- HIV diagnosis: incidence proportion and incidence rates between index date and the 1st discontinuation
- STI testing/screening
  - Assessed during the first period of PrEP use (oral or injectable)
    - Incidence proportion and incidence rate for STI testing/screening for
      - Gonorrhea
      - Chlamydia
      - Syphilis
      - Chancroid
      - Lymphogranuloma venereum
      - *Mycoplasma genitalium*
      - Hepatitis B virus (HBV)
      - Hepatitis C virus (HCV)
      - Genital Herpes (HSV-1, HSV-2)
      - Trichomoniasis
      - Genital Human papilloma virus (HPV) including warts
    - Interval between the first 2 tests for gonorrhea, chlamydia, syphilis done during the first period of PrEP use
      - Testing 3 months (76-104 days) after last test
      - Testing 6 months (168-196 days) after last test
      - Testing 12 months (351-379 days) after last test
- STI diagnoses
  - New diagnosis of STI as noted in medical record or positive test result
  - STI diagnoses for
    - Syphilis
    - Gonorrhea
    - Chlamydia
    - Chancroid
    - Lymphogranuloma venereum
    - *Mycoplasma genitalium*
    - Hepatitis B virus (HBV)
    - Hepatitis C virus (HCV)
    - Genital Herpes (HSV-1, HSV-2)
    - Trichomoniasis
    - Genital Human papilloma virus (HPV) including warts
- Relevant prescription for a selected list of STIs  
 Proportion of STI diagnosis with a prescription within 14 days following diagnosis as follows:
  - Syphilis: benzathine penicillin G, aqueous crystalline penicillin G, procaine penicillin G + probenecid, doxycycline
  - Gonorrhea: ceftriaxone, ceftriaxone + doxycycline, gentamicin + azithromycin,

- cefixime, cefotaxime
- Chlamydia: doxycycline, azithromycin, levofloxacin, amoxicillin
- Chancroid: azithromycin, ceftriaxone, ciprofloxacin, erythromycin base
- Lymphogranuloma venereum: doxycycline, azithromycin, erythromycin base
- *Mycoplasma genitalium*: doxycycline + azithromycin, doxycycline + moxifloxacin
- Trichomoniasis: metronidazole, tinidazole

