##### **Veterans using PrEP (Objective set 3)**

**Objective 3.1-** Baseline demographic and clinical characteristics will be described at the start of PrEP use during the study period, by regimen type (oral or CAB LA), using median and interquartile ranges for continuous variables and counts and proportions for categorical variables.

**Objective 3.2-** The proportions of Veterans on care initiating CAB LA PrEP who used oral lead in (OLI) and proportion of those with direct to injection (DTI) will be calculated.

**Objective 3.3 and 3.4-** PrEP adherence and usage patterns will be described using median and interquartile range for continuous data as well as absolute and relative frequencies for categorical data. The percentage of days with access to oral PrEP and CAB LA PrEP will be described over the first 12 months after index PrEP initiation. Characteristics of individuals with and without delayed CAB LA injections as well as individuals with and without discontinuation will be compared using Pearson's chi-square tests for categorical variables and Mann-Whitney tests for continuous variables.

**Objective 3.5-** Incidence rates and confidence intervals for HIV testing, HIV diagnosis, STI testing/screening and STI diagnosis will be calculated using univariate Poisson regression. STI treatment prescription will be described using absolute and relative frequencies for categorical data.

**Objective 3.6-** For CAB LA PrEP users diagnosed with HIV, a timeline including details of oral PrEP prescriptions prior to CAB LA PrEP start, injections received, HIV tests performed, HIV treatment, viral load measurements, HIV drug resistance will be provided for each individual.

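### The STI retest interval needs two tests inside the first period of PrEP use, so it omits users never retested and cuts off long intervals at an end of use that differs by modality

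*Protocol*

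**What the plan says.** Section 7.3.3 of the Protocol, under STI testing/screening for Objective 3.5, lists two kinds of measure for the first period of PrEP use. One is the incidence proportion and incidence rate of testing for each STI. The other is the "Interval between the first 2 tests for gonorrhea, chlamydia, syphilis done during the first period of PrEP use", with three categories: "Testing 3 months (76-104 days) after last test", "Testing 6 months (168-196 days) after last test" and "Testing 12 months (351-379 days) after last test". There is no category for users without a second test, no stated denominator for the windows, and no rule for a first period that ends before a second test.

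The first period ends differently by modality. For oral PrEP, section 7.3.3 gives two discontinuation rules: "Oral PrEP prescription not refilled within 30 days of the previous dispensing" and "Oral PrEP prescription not refilled within 90 days of the previous dispensing". For CAB LA, the discontinuation date is 127 days after the last injection. Section 7.1 ends the study on 31 December 2025.

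Objective 3.5 (section 6) reports STI testing by modality. For this objective, section 7.7.1.1 names Poisson rates and frequencies of STI treatment. It names no method for intervals that are cut off.

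**The concern.** The interval is the only measure in the plan that shows whether STI screening follows a 3-, 6- or 12-month rhythm. By definition it exists only for users who were retested before their first period ended. Users tested once and never again, who are the gap in screening that such a measure should show, contribute nothing to it. Among the rest, a long interval is recorded only if use lasted long enough to contain it. Short intervals are kept and long ones are lost, and the loss is greater where use is shorter.

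If oral and CAB LA users stay on PrEP for different lengths of time, their interval figures will differ when set side by side even if clinics retest both groups identically.

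**Working it through.** The Protocol gives no expected value for the interval, so there is no figure to reproduce. The check has two parts: limits that follow from the plan's own dates and rules, and an illustration on assumed durations.

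**1. Limits fixed by the plan.**
- Study end: 31 December 2025 minus 351 days is 14 January 2025. A CAB LA user who starts after that date cannot enter the 351–379 day window. Section 7.2.1 admits CAB LA users until 30 June 2025, which leaves 184 days.
- Section 7.2.1 admits oral users until 31 December 2024, which leaves 365 days. (Section 7.1 gives 30 June 2025 for PrEP initiation in general; the two dates need reconciling.)
- End of use: if an oral period is taken to end 30 or 90 days after the last dispensing (an assumption, since the end date is not written out), a user with one dispensing can show an interval of at most 30 or 90 days. The first misses the 76–104 day window altogether; the second reaches only days 76–90. A CAB LA period runs 127 days past the last injection.

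**2. Illustration with identical testing in both groups.** Assumptions: time from first to second test is exponential with mean 8 months; remaining use after the first test is exponential with mean 8 or 14 months; a month is 30.4375 days. Per day, the retest rate is λ = 1/(8 × 30.4375) = 0.004107. The stopping rate is μ = 0.004107 or 1/(14 × 30.4375) = 0.002347. The sum s = λ + μ is 0.008214 or 0.006453.

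- Share with a second test in the period, λ/s: 0.500 and 0.636. So 50% and 36% of first-tested users have no interval.
- Share of observed intervals ≤104 days, 1 − exp(−104s): 57% and 49%. True share, 1 − exp(−104λ): 35%.
- Median observed interval, ln 2/s: 84 and 107 days. True median, ln 2/λ: 169 days.
- Share in a window from a to b days among users with two tests, exp(−s(a − 0.5)) − exp(−s(b + 0.5)). The true share uses λ in place of s. With all first-tested users as denominator, multiply by λ/s.

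| Window (days) | Two tests: use 8 / 14 months | All first-tested: use 8 / 14 months | True |
|---|---|---|---|
| 76–104 | 11.4% / 10.5% | 5.7% / 6.7% | 8.2% |
| 168–196 | 5.4% / 5.8% | 2.7% / 3.7% | 5.6% |
| 351–379 | 1.2% / 1.8% | 0.6% / 1.1% | 2.7% |

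Among users with two tests, the largest distortion is 11.4 − 8.2 = 3.2 points and the largest difference between groups is 11.4 − 10.5 = 0.9 points. The 12-month window is understated in both groups.

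**3. A second model.** Retest times are Weibull (shape 1.5, median 182 days among those ever retested), 30% are never retested, and median remaining use is 90, 180, 365 or 730 days. The median observed interval is 94, 127, 151 and 165 days. The share of observed intervals ≤104 days is 55%, 41%, 33% and 30%, while 18.1% of all first-tested users are truly retested by then. With nobody permanently unretested, the 76–104 day share among observed pairs is 14.4%, 12.3%, 10.7% and 9.7% against a true 8.8%. The direction is the same; the size moves with the durations assumed.

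**4. Which estimator removes the dependence.** Kaplan-Meier from the first test, censored at the end of the first period, returns 18.1% by day 104 at all four durations in the second model. In the first model it recovers the true 34.8%, 55.3% and 78.9% at days 104, 196 and 379 in both groups. Treating discontinuation as a competing event gives (λ/s)(1 − exp(−st)): 28.7% vs 31.1%, 40.0% vs 45.7% and 47.8% vs 58.1%. That still depends on duration of use.

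**The case against.** The strongest reply is that the main testing measures already keep everyone. The incidence proportion and rate of STI testing do not require a second test, and users never retested contribute person-time to the rates. That stands: the loss is confined to the interval. But a user tested once counts as tested in the proportion, and a rate does not show the 3-, 6- or 12-month rhythm.

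A second reply is that the study is descriptive and plans no test of this interval between modalities. That also stands. The harm is a misleading side-by-side description, not a wrong test.

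A third is that an unstated denominator is a table detail for the statistical analysis plan. That holds for the denominator alone. The requirement of two tests inside the first period is in the Protocol's definition, and changing the denominator does not cure it: with all first-tested users, the shares are too low and still depend on duration.

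A reader might infer from the ≤104-day figures that the plan's results would be overstated by 14 to 23 points (49% and 57% against 35%), with a false 9-point gap between modalities. The documents do not support that, because ≤104 days is not one of the plan's categories. A reader might also infer that the modality with shorter use always looks better. In the 76–104 day window it looks better among users with two tests (11.4% vs 10.5%) and worse among all first-tested users (5.7% vs 6.7%), and the plan does not say which applies.

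**Conclusion.** The point holds for the interval measure. As defined, it leaves out users without a second test, right-truncates intervals at the end of the first period, and depends on duration of use and on modality-specific rules for when use ends. The direction for the raw interval (too short) follows from the definition and does not rest on the models. For CAB LA starters after 14 January 2025, the 12-month window is closed by the calendar alone.

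The size is not known, because the plan gives no durations of use. In the exponential model, the plan's own windows are off by at most about 3 points and the modalities differ falsely by about 1 point. The second model shows a larger distortion when use is short. The effect on the median interval is larger than on the windows (84 and 107 days against 169). Both models assume that stopping PrEP is unrelated to when the next test would have occurred.

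**What to change.** In section 7.3.3, for each of the three STIs and each modality:

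- Take all users with a first test in the first period as the denominator, and report how many had no second test in that period.
- Estimate time from first to second test by Kaplan-Meier, censored at the end of the first period (discontinuation, study end, loss to follow-up, death or HIV diagnosis). Report the cumulative proportion retested by days 104, 196 and 379, the upper bounds of the plan's windows.
- State the assumption that stopping is non-informative, and say which oral refill rule ends the first period for this analysis.
- If retesting while still on PrEP is also of interest, report the competing-event cumulative incidence separately and label it as dependent on duration of use.
- Keep the raw intervals and windows as a secondary description, labelled as conditional on two tests.

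The cost is one extra standard analysis on data already extracted, and a retest figure that will look less favourable.

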  - Proportion of CAB LA PrEP users with at least one maintenance injection who are on CAB LA PrEP at 12 months and 24 months after initiation and at the end of the study period
- 3.5- Described patterns of HIV and other STI testing/screening, diagnosis and STI treatment
- a) Assess the incidence of HIV testing and HIV diagnosis during the first period of PrEP use by PrEP modality
  - b) Estimate the frequency of testing for STI diagnosis and STI diagnosis by PrEP modality
    - in the 6 months preceding PrEP initiation
    - during the first period of PrEP use
  - c) Describe the proportion of diagnosed STI with a relevant antimicrobial prescription
- 3.6- Among CAB LA PrEP users diagnosed with HIV (during CAB LA PrEP use or after CAB LA PrEP discontinuation)
- a) Describe the timing of incident HIV diagnoses relative to timing of CAB LA PrEP usage and testing for HIV
  - b) Describe adherence to PrEP injection schedule, HIV treatment, virologic suppression, concomitant STI diagnosis, and HIV drug resistance

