#### **7.3.2. Baseline characteristics**

The following variables will be assessed for objectives 2.1 and 3.1 at index date:

- **Demographic characteristics**

- Age (years)
- Birth sex
- Race (American Indian or Alaska Native, Asian, Black or African American, Native Hawaiian or Pacific Islander, White, Not reported)
- Ethnicity (Hispanic, not Hispanic)
- Geographic Region (Northeast, Midwest, South, West, US Territories)
- Rurality (Highly rural, Rural, Urban)
- Marital/Relationship status
- Homelessness in the past 12 months

- **Clinical characteristics**

- Number of outpatient visits in the 12 months prior to index date
- Number of primary care outpatient visits in the 12 months prior to index date
- Comorbidity burden using the Charlson Comorbidity Index
- PrEP prescriber specialty
- Psychiatric diagnoses (major depression, bipolar disorder, post-traumatic stress disorder - PTSD, schizophrenia)
- Substance use (smoking, alcohol use disorder, injection and non-injection illicit drug use disorder)
- BMI

- VACS Index 2.0
- **Sexual Behavior and Health**
  - History of STI (ever)
    - Syphilis
    - Gonorrhea
    - Chlamydia
    - Chancroid
    - Lymphogranuloma venereum
    - *Mycoplasma genitalium*
    - Hepatitis B virus (HBV)
    - Hepatitis C virus (HCV)
    - Genital herpes – Herpes Simplex Virus (HSV) 1 or 2
    - Trichomoniasis infection
    - Genital Human papilloma virus (HPV) including warts
  - History of STI (past 3 months)
    - Syphilis
    - Gonorrhea
    - Chlamydia
    - Chancroid
    - Lymphogranuloma venereum
    - *Mycoplasma genitalium*
    - Hepatitis B virus (HBV)
    - Hepatitis C virus (HCV)
    - Genital herpes
    - Trichomoniasis infection
    - Genital Human papilloma virus (HPV) including warts
  - History of PrEP use

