### 7.3.3. Outcome definitions

#### ◆ Veterans without HIV (Objective 1)

Incident HIV diagnosis: a new HIV diagnosis is defined as either having a (1) positive screening antibody test with positive confirmatory antibody testing, (2) positive HIV viral load, or (3) documentation of HIV on the EHR problem list.

All potential HIV incident diagnosis will be subject to a detailed review for confirmation.

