#### ◆ People without HIV who are not on PrEP and could benefit from PrEP (Objective set 2)

##### ◆ HIV testing & STI screening (Objective 2.2)

- HIV testing
  - Frequency and rate of HIV tests over 12-month period following the index date

- Type of HIV tests
- HIV diagnoses
  - Frequency and rate of new HIV diagnosis within 12 months of index date (first visit with at least one criteria for PrEP)  
Follow-up (FU) will be censored at first of:
    - HIV diagnosis
    - 12 months after index date
    - End of the study period
    - Loss to follow-up
    - Death
- STI testing/screening
  - Frequency and rate of STI testing events, overall (testing for multiple STIs on the same day will count as 1 testing event) and by type of STI tested  
Type of STI:
    - Syphilis
    - Gonorrhea
    - Chlamydia
    - Chancroid
    - Lymphogranuloma venereum
    - *Mycoplasma genitalium*
    - Hepatitis B virus (HBV)
    - Hepatitis C virus (HCV)
    - Genital Herpes (HSV-1, HSV-2)
    - Trichomoniasis
    - Genital Human papilloma virus (HPV) including warts  
Follow-up (FU) will be censored at first of:
    - HIV diagnosis
    - 12 months after index date
    - End of the study period
    - Loss to follow-up
    - Death
- STI diagnoses
  - Frequency and rate of new diagnosis of STI as noted in medical record or positive test result
  - STI diagnoses for
    - Syphilis
    - Gonorrhea
    - Chlamydia
    - Chancroid
    - Lymphogranuloma venereum
    - *Mycoplasma genitalium*
    - Hepatitis B virus (HBV)
    - Hepatitis C virus (HCV)
    - Genital Herpes (HSV-1, HSV-2)
    - Trichomoniasis

- Genital Human papilloma virus (HPV) including warts

◆ **PrEP users (Objective set 3)**

◆ **Use of oral lead-in (Objective 3.2)**

CAB PrEP formulation at initiation: proportion with CAB oral lead-in (OLI) vs. direct to injection (DTI)

◆ **Adherence (Objective 3.3)**

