##### **Veterans who are not on PrEP and who could benefit from PrEP (Objective set 2)**

Baseline demographic and clinical characteristics will be described at the first visit during the study period meeting one of the criteria (index date), using median and interquartile ranges for continuous variables and counts and proportions for categorical variables. The frequency and rate (per 100 person-years) of HIV testing, HIV diagnoses, STI testing/screening, and STI diagnoses will be described within 12-months of the index date.

Rates of HIV tests and diagnoses as well as STI tests and diagnoses over this 12-month period will be estimated using univariate Poisson regression

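### A positive test alone can qualify as a new STI diagnosis, so infections with long-lasting markers can be counted as incident

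*Protocol*

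**What the plan says.** Section 7.3.3 defines the STI diagnosis outcome twice, in nearly the same words. For PrEP users (Objective 3.5) it is "New diagnosis of STI as noted in medical record or positive test result". For Veterans not on PrEP (Objective 2.2) it is "Frequency and rate of new diagnosis of STI as noted in medical record or positive test result". Each definition is followed by the same 11 infections: syphilis, gonorrhea, chlamydia, chancroid, lymphogranuloma venereum, *Mycoplasma genitalium*, HBV, HCV, genital herpes, trichomoniasis and genital HPV.

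Section 7.7.1.1 turns these counts into rates. For Objective 3.5: "Incidence rates and confidence intervals for HIV testing, HIV diagnosis, STI testing/screening and STI diagnosis will be calculated using univariate Poisson regression". For Objective set 2: "Rates of HIV tests and diagnoses as well as STI tests and diagnoses over this 12-month period will be estimated using univariate Poisson regression". Objective 3.5b in Section 6 also asks for the outcome "in the 6 months preceding PrEP initiation", alongside the first period of use. For a selected list of infections, Objective 3.5c takes STI diagnoses as the denominator for a relevant prescription within 14 days.

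Section 7.3.2 collects STI history for the same 11 infections, both lifetime and over the past 3 months, but only as a baseline descriptor.

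**The concern.** An incidence rate needs two things: events that really are new, and person-time from people who could have had one. The definition uses the word *new* but gives it no content. As written, a positive result is enough. For several of the listed infections a test can remain positive long after the infection began or was treated. This is general laboratory knowledge, not a statement in the protocol. A Veteran with an old infection who is routinely retested after the index date meets the definition. A Veteran with a known chronic infection who is not retested still contributes person-time.

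STI diagnosis is a main outcome in the synopsis and an endpoint for Objective sets 2 and 3 in Table 2. At stake is whether the rows for the persistent-marker infections can be read as incidence, and whether the 3.5c proportion for syphilis and genital herpes can be read as treatment of new disease.

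**Working it through.** **1. No stated figure to reproduce.** The protocol gives no STI rate, marker prevalence or retest share. The check is of the definition; the arithmetic only shows direction and range.

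**2. HIV and STI rules side by side.**

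| | Incident HIV | New STI diagnosis |
|---|---|---|
| Prior infection excluded | Yes, cohorts require no evidence of HIV (7.2.1) | No |
| Qualifying test named | Yes, confirmed antibody test or viral load; problem-list entry also accepted (7.3.3) | No, any positive result |
| Case confirmation | "All potential HIV incident diagnosis will be subject to a detailed review for confirmation" | None |
| Rule for repeat positives | Prior infection excluded, so not needed | None |

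Section 7.3.3 does set counting rules elsewhere. Under Objective 2.2, same-day tests for several STIs make one testing event. Under Objective 3.3, each calendar day of coverage counts once. Neither rule reaches diagnoses. Section 7.9 does not list the issue as a limitation.

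**3. Which infections are affected.**
- Marker can persist: HBV, HCV, HSV-1/2, syphilis serology, possibly HPV. Old infection can be counted as new.
- Gonorrhea, chlamydia, trichomoniasis, *M. genitalium*: only repeat positives within one episode.

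**4. Numerator, illustrated.** Let *r* be genuinely new events per 100 person-years over all person-time, *p* the share with an old persistent marker, *s* the share of those retested in the period, *q* = *p* × *s*, and *T* the mean period in years. Counting each old positive once:

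recorded rate = *r* + 100*q*/*T*, and spurious events = *N* × *q*.

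Only *N* = 748 CAB LA users comes from the protocol (Section 7.5); everything else is assumed.
- *p* = 5%, *s* = 50%: 748 × 0.05 × 0.5 = 18.7 events.
- *p* = 20%, *s* = 50%: 748 × 0.20 × 0.5 = 74.8 events.
- With *r* = 10 and *T* = 1, *q* of 2%, 5%, 10% or 20% gives a recorded rate of 12, 15, 20 or 30.
- Smallest ratio of recorded to true rate in the range examined: *r* = 30, *q* = 2%, *T* = 1, (30 + 2)/30 = 1.07.
- Largest: *r* = 2, *q* = 20%, *T* = 0.5, (2 + 40)/2 = 21.

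The distortion is greatest for low-incidence chronic infections and short windows. The pre-initiation window in Objective 3.5b is one with *T* = 0.5.

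**5. Denominator.** Suppose *new* were honoured in the numerator but people already infected, and so not at risk, stayed in the person-time. A rate of 10 among those at risk would be reported as 10 × (1 − *p*): 9.5 at *p* = 5% and 8.0 at *p* = 20%. This error runs the other way, so both parts need a rule.

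**6. Objective 3.5c.** Assume 90% of new cases and none of the old positives receive a listed prescription within 14 days, with *r* = 10 and *T* = 1. The treated share is 0.9 × 10/(10 + 100*q*), which is 75%, 60%, 45% or 30% for *q* = 2%, 5%, 10% or 20%. Of the persistent-marker infections, only syphilis and genital herpes are on the 3.5c list; HBV, HCV and HPV are not.

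**The case against.** The strongest reply is that *new* is the condition, and that the record entry and the positive test are merely its two sources. On that reading nobody intends to count an old infection, and assays, look-back and episode gaps belong in an SAP that is not shown. The intent is clear, and the protocol nowhere says that antibody results will qualify. But Section 7.3.3 goes beyond silence: it makes a positive result sufficient for every infection on the list, and an SAP asking for more would narrow the protocol's own definition. The contrast with HIV in the same section shows that such rules were thought to belong at this level.

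Other parts of the reply stand, and they rule out stronger readings that a reader might infer:
- **Every positive counts, at every retest, even vaccine-induced HBV antibody.** The word *new* argues against this. The text fails to exclude it but does not call for it.
- **Inflation differs between CAB LA and oral PrEP.** The 2-month and 3-month visits in Section 5 concern HIV tests, refills and injections. No STI testing interval there differs by modality, and the 3-, 6- and 12-month STI intervals in 7.3.3 are common to both. If 90% of old positives were retested in one group and 50% in the other, with an equal true rate of 10, marker prevalence 2–20% and *T* of 0.5 to 1 year, a spurious rate ratio of 1.07 to 1.53 would appear. That split is invented. The bias is possible, not shown, and no formal comparison of STI rates between modalities is planned.
- **All STI incidence in the study is a mixture with prevalence.** Diagnoses are listed by infection, so errors in the HBV, HCV or herpes rows do not enter the gonorrhea or chlamydia rows.

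**Conclusion.** The concern holds in limited form. As written, the definition lets prevalent infection count as incident for HBV, HCV, HSV-1/2, syphilis and possibly HPV, and keeps people not at risk in the person-time for Objectives 2.2 and 3.5. It can understate the 3.5c proportion for syphilis and genital herpes. For gonorrhea, chlamydia, trichomoniasis and *M. genitalium*, only repeat positives within an episode are at issue.

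The size is undetermined: the ratio of 1.07 to 21 reflects the assumed inputs, not evidence from the protocol. The conclusion rests on two premises: some markers persist, and results of that kind are not excluded. A reader might infer that most chronic viral events will be prevalent, or that the STI results as a whole are unusable; the protocol supports neither. This should be fixed, but it affects some rows of descriptive tables and does not threaten the study.

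**What to change.** In Section 7.3.3, replace the single rule with one by type of infection:

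1. **HBV, HCV, genital herpes, HPV:** restrict the at-risk set to people with no record or positive result before the start of the window; count the first event only; do not let antibody positivity alone qualify.
2. **Syphilis:** in a person with a prior reactive result or diagnosis, do not let a reactive test alone qualify. Require evidence of a new episode under a pre-specified criterion chosen by the investigators.
3. **Other curable STIs:** set a fixed episode interval so that repeat positives within it count once.
4. **Objective 3.5c:** use the same episodes as the denominator.

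Apply the rules identically to Objective 2.2 and to both windows of Objective 3.5b. The cost is protocol wording and some programming on laboratory and history data already in scope, with a few true reinfections not counted. It is best settled before programming; Section 4 schedules the results tables for Q2 2027.
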